30   Two conditions: 1)a-tDCS (2mA for 20 minutes) will be applied over the left DLPFC followed  
31   immediately by behavioral naming therapy and 2) sham tDCS followed immediately by  
32   behavioral naming therapy will be presented to participants with non-fluent aphasia. *Hypothesis*  
33   1: no adverse events will be reported during or following this treatment and all participants will  
34   complete the study.  
35

36   **Aim 2:** *Identify effectiveness of a-tDCS to the left DLPFC combined with behavioral naming*  
37   *treatment in Broca's aphasia and establish a sample size for future investigations of this nature.*  
38   A small sample size will be used in this study to investigate effectiveness of the use of a-tDCS  
39   to the left DLPFC with behavioral therapy to target naming in non-fluent aphasia. *Hypothesis 2:*  
40   Improvements in working memory, naming reaction time and naming accuracy will be observed  
41   after the real a-tDCS condition but not after the sham a-tDCS condition.  
42

1     • **Is the primary outcome (and secondary outcomes, as appropriate) clearly  
2     defined?**

3     Primary outcomes include: naming accuracy on treated and control items, naming RTs on  
4     treated and control items, performance on WM tasks, and motor speech tasks.

5     • **Are there adequate preliminary data in the literature (or from the investigator) to  
6     justify the proposed research? Has an adequate literature review been done to  
7     support this study?**

8  
9     WM systems are short-term, temporary stores that are activated when active manipulation of  
10    items is necessary. It could be argued that all linguistic tasks invoke WM systems since the  
11    execution of any linguistic task requires the ability to maintain activation of a representation until  
12    the targeted linguistic process is complete. Indeed, the close relationship between language  
13    and WM is represented in many WM models. Over the past few decades, there has been  
14    increasing recognition that aphasia is frequently accompanied by deficits in WM systems.  
15    Furthermore, such deficits adversely impact linguistic performance in aphasia. Accordingly,  
16    treatment protocols are being developed on the premise that treatments aimed at improving WM  
17    systems will improve linguistic function in aphasia. While a variety of WM treatment  

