46    relationship to emotional well-being and functional communication, treatment that  
47    improves naming deficits will positively influence quality of life in many of these individuals.  
48    The approach taken to remediate naming deficits in aphasia is to treat impaired WM systems

1 on the premise that certain cognitive processes underlie linguistic functions in aphasia. This  
2 approach represents a departure from most behavioral-based naming treatment approaches,  
3 but reflects a growing recognition that WM systems in individuals with aphasia impact  
4 linguistic performance . The addition of a-tDCS as a neuromodulation tool to increase  
5 cortical excitability (upregulate) the working memory center to target naming is a novel  
6 approach in aphasia. These findings, , will provide valuable information regarding the role  
7 WM plays in naming and the potential benefit of using neuromodulation to the DLPFC to  
8 influence naming in aphasia.

9

- 10 • **Is the design of the study appropriate for the questions that are posed?**

11

12 *Treatment Design:*

13 A single subject cross-over design with a 4 week wash out period will be used. Two treatment  
14 conditions will be presented. The sham (SHAM) condition will consist of presentation of sham  
15 tDCS for 20 minutes followed by behavioral naming treatment. The real treatment condition  
16 (REAL) will consist of 20 minutes of a-tDCS to the left DLPFC followed by behavioral naming  
17 treatment. The length of behavioral naming treatment will depend on how long each participant  
18 takes to go through the treatment stimuli twice. A SHAM-REAL sequence will be used across all  
19 participants. Although order effects may be introduced using the same sequence across  
20 participants, the small number of participants makes it difficult to interpret any data that comes  
21 from using a counterbalanced presentation of treatment.

22 Treatment will be provided over five consecutive days. A minimum of a one-month washout  
23 period will be provided between the two conditions (Figure 1). Prior to initiating the REAL  
24 treatment condition, the naming RTs obtained on the second word list during the pre-treatment  
25 testing period (prior to the initiation of the SHAM condition) will be compared to the naming RTs  
26 obtained after the washout period. RTs will be analyzed to ensure that no lasting treatment  

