27 effects remain after the SHAM condition. If performance on naming RTs is +/- 1 standard  
28 deviation from the individual's benchmark mean, the REAL treatment condition will begin. If  
29 performance on naming RTs is > +/- 1 standard deviation from the individual's benchmark  
30 mean, REAL treatment will be postponed until the mean RTs fall within +/- 1 standard deviation  
31 of the benchmark. Periodic checks will be conducted weekly to identify when to begin REAL  
32 condition. Once there are minimal differences between naming RTs on the second word list,  
33 the REAL treatment will be initiated.

34

[figure not shown]
35 *Outcome measures:*

36 Two different word lists will be generated; a different list will be used for each treatment  
37 condition to control for exposure and learning effect. Pretreatment testing outcome measures will  
38 be recorded for 5 consecutive days for each outcome measure including: 1) naming accuracy 2)  
39 naming RTs on both word lists 3) performance on motor speech tasks and 4) performance on  
40 working memory tasks. Stability of baseline performance, defined as no more than 20%  
41 difference between scores, will be obtained in five consecutive sessions. In addition, outcome  
42 measures will be obtained immediately after each treatment session. Five maintenance  
43 outcome measures will also be obtained upon completion of treatment. These sessions will take  
44 place at the Clinical Translational Science Institute (CTSI) on [name] on the University  
45 of MN campus. An adverse events questionnaire will also be given after each treatment session  
46 as a mechanism of participants reporting any discomfort.

47  
48  
49

50

1 **Figure 1. Treatment Schedule**

6 *tDCS Protocol.*

7 Treatment sessions will take place at the University of MN Clinical Translational Science  
8 Institute. Each participant will be seated comfortably in a chair. A swim cap will be placed on  
9 the participant's head to identify cranial landmarks for accurate electrode placement. The area  
10 referred to as F3 by the International 10/20 system for electroencephalogram electrode  
11 placement has been established as the optimal location for targeting the left DLPFC.  
12 The F3 region will be located by marking the vertex (the midpoint between left and right tragus  
13 and midpoint between nasion and inion), measuring the head circumference. When these  

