5 and word length. Familiarity ratings will be obtained from a normative database. Visual  
6 complexity ratings will be also obtained from a group of 20 individuals using the instructions and  
7 rating scales as reported in Snodgrass and Vanderwart's article. The CELEX database, will  
8 be consulted to determine lexical frequency of the words (cues) used in the study. An additional  
9 40 pictures will be selected for a control (untreated) list that will be used only during baseline  
10 and post-treatment testing. Performance on treated and untreated lists will be compared to  
11 determine treatment effects and possible generalization effects.

12  
13 *Naming Treatment Procedures.* All participants will be provided the same protocol, which will  
14 highlight the process of rehearsing the cues associated with the picture name. Treatment  
15 sessions will last until each participant has gone through the treated items twice. To insure  
16 control during the protocol, a graduate student trained in the protocol will administer the  
17 treatment steps. She will be blinded to the objectives of the study and conditions that are being  
18 administered. Treatment sessions will be video recorded for reliability purposes. To insure that  
19 she is not aware of when tDCS is being administered, a screen will be in place between the  
20 tDCS machine and the treatment table. The protocol is provided in Table 1.

21  
22 **Table 1. Naming Treatment Protocol.**

Steps Involved in Naming Treatment Protocol	
Picture Presentation	Participant will be asked to name the picture. If she/he is unable to provide the name within 10 seconds, the name will be provided.
Cue Presentation	Cues that accompany the picture will be presented. He/she will be asked to read each cue word as it is presented. If he/she is unable to read the word spontaneously within 10 seconds, he/she will be asked to repeat each word after the clinician.
Cue Rehearsal	Both picture and cues are taken away. Participant is asked to rehearse the cue words silently for 10 seconds.
Cue Self-Generation	Participant will be asked to generate all three cues. For each instance that the participant is unable to provide a cue within 10 seconds, the cues will be provided. Once the cues have been provided, the participant will then be asked to provide the picture name.

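### Hypothesis 2 predicts gain after REAL and none after SHAM, although SHAM contains the same naming therapy, and no REAL-minus-SHAM difference in change is defined

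*Combined protocol and SAP*

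**What the plan says.** - **Hypothesis (aims section, Aim 2).** Improvement in working memory, naming reaction time (RT) and naming accuracy is expected "after the real a-tDCS condition but not after the sham a-tDCS condition". Improvement is not defined. The same aim intends to "establish a sample size for future investigations of this nature".
- **Conditions (Treatment Design).** SHAM is sham "tDCS for 20 minutes followed by behavioral naming treatment. The real treatment condition" replaces the sham current with a-tDCS and keeps the therapy. Treatment runs over five consecutive days, and Naming Treatment Procedures gives one protocol for everyone.
- **Order and lists.** "A SHAM-REAL sequence will be used across all" participants. Outcome measures adds: "Two different word lists will be generated; a different list will be used for each treatment" condition.
- **Washout check (Treatment Design).** Before REAL starts, second-list "RTs will be analyzed to ensure that no lasting treatment" "effects remain after the SHAM condition".
- **Analysis (statistical considerations, Aim 2).** For RT, working memory and motor speech, each participant's means and 95% intervals are plotted and compared across conditions. RT changes within and across conditions are inspected visually. Naming accuracy gets an effect size, read against 4.0, 7.0 and 10.1 as small, medium and large.
- **Other comparisons.** The Stimuli section says "Performance on treated and untreated lists will be compared to" judge treatment and generalization effects. The section on whether the measures are necessary says that effects will be compared with sham visually and graphically.

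**The concern.** SHAM is active therapy without active current. A hypothesis about what a-tDCS adds should therefore concern the difference between two gains. Hypothesis 2 instead joins two separate statements: a gain in one condition and no gain in the other.

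Two problems follow from that wording. If the therapy works in both conditions, the hypothesis fails as written even when the REAL gain is clearly larger. If the SHAM gain is modest, one condition can appear to improve and the other not, through session-to-session noise alone. Only when the SHAM gain is near zero does the wording serve well. The background section offers a reason why it might be small (deficient subvocal rehearsal in aphasia), but this is not known in advance.

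The sample-size intention in Aim 2 is also affected. A later trial of REAL against SHAM needs the difference and its spread between participants. The planned data would allow both to be computed, but the plan does not say that they will be.

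**Working it through.** **What is defined.** The plan states no power or sample-size calculation for its four participants, so there is no figure to reproduce. Of the planned analyses, the plotted intervals describe condition means, the accuracy effect size and its benchmarks describe the size of a treatment effect, the list comparison sets treated against untreated items, and the washout check decides when REAL may start. None is (REAL change) − (SHAM change), a difference between two effect sizes, or an interval for either.

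**Illustration: assumptions.** One outcome in one participant; 5 pre and 5 post scores per condition, independent and normal with session SD 1; equal true baselines. The five pre-treatment days and five treatment days come from the plan. The rules and gains below are assumed, because the plan states none. Rates are from simulation, with at least 200,000 runs per setting.

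*Rule A, the literal wording of Hypothesis 2:* improved means that the 95% t-interval for post − pre (8 df) lies above 0; the pattern is REAL improved and SHAM not improved.

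*Rule B, one reading of the planned interval comparison:* the post-REAL 95% interval lies wholly above the post-SHAM one.

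*Rule C, the direct contrast:* the 95% interval for (REAL post − REAL pre) − (SHAM post − SHAM pre) lies above 0. SE = s√(4/5) = 0.894s, 16 df. If one baseline serves both conditions, the contrast reduces to REAL post − SHAM post, with SE = s√(2/5) = 0.632s, 12 df.

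| SHAM gain (SDs) | 0 | 0.5 | 1 | 1.5 | 2 | 2.5 | 3 |
|---|---|---|---|---|---|---|---|
| A, no a-tDCS effect | 2.5% | 9% | 20% | 25% | 17% | 6% | 1.5% |
| A, 2-SD benefit | 77% | 83% | 70% | 45% | 21% | 7% | 1.5% |

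Rules B and C do not depend on the SHAM gain:

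| | No effect | 2-SD benefit |
|---|---|---|
| B | about 0.3% | about 36% |
| C, separate baselines | 2.5% | about 55% |
| C, shared baseline | 2.5% | about 83% |

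**Checks by formula.**
- Rule A with equal gains: if each condition is judged improved with probability p, the pattern has probability p(1 − p), at most 0.5 × 0.5 = 25%.
- Rule B with equal standard errors: non-overlap requires a difference of 2 × 1.96/√2 = 2.77 standard errors of the difference. That is a two-sided level of about 0.0056, or 0.3% in the direction of REAL.

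**Limits of the direct contrast.**
- Half-width with separate baselines: 2.12 × 0.894 = 1.90 session SDs at s = 1 (simulated mean 1.87). With a shared baseline: 2.18 × 0.632 = 1.38 (simulated mean 1.35).
- Lag-1 autocorrelation of 0.2, 0.4 or 0.6, if ignored, lowers coverage to 90%, 80% or 67%.
- A 1-SD shift from order, practice or word list makes it favour REAL in 18% of cases (31% with a shared baseline).
- An SD estimated from four participants has a 95% range of √(3/9.348) = 0.57 to √(3/0.2158) = 3.73 times the estimate. Sample size goes with the square, so the factor is 0.32 to 13.9.

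**The case against.** The strongest reply is that Hypothesis 2 is a prediction and not a decision rule. Nothing in the statistical section says that it will be judged by Rule A, and no interval for a within-condition change is planned. What is planned is a comparison across conditions for each participant, and Rule B is at least as close to that text as Rule A. Under Rule B the reading is conservative and indifferent to the SHAM gain. This stands.

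A reader might therefore infer too much in three ways:
- *That the plan never compares REAL with SHAM.* It does, by plots, intervals and visual inspection.
- *That the analysis as a whole misleads in either direction, with false patterns in up to 25%.* That applies to the wording of the hypothesis under an assumed rule. It is not a property of any rule in the plan.
- *That the washout check shows that SHAM gains are expected on treated items.* It uses second-list RTs, a list not treated under SHAM, and is a precaution against carry-over.

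The chance pattern also fades when gains are large. If the accuracy benchmarks are in baseline-SD units (an assumption), even a small effect of 4.0 lies beyond the gains in the table, and at a shared gain of 4 SDs Rule A gives a false pattern in about 0%. For accuracy, what remains is that the hypothesis would be contradicted by a SHAM gain.

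Finally, the primary purpose is feasibility and safety, with four participants and a single-subject design, and the plan acknowledges possible order effects. A formal interval on a fixed-order contrast could suggest more precision than exists, so it needs a plain caveat. None of this answers the point that the stated prediction does not match the question.

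**Conclusion.** The point holds in a limited form, and its severity is minor. From the text alone: both conditions contain the same therapy, Hypothesis 2 predicts no SHAM gain, and no REAL-minus-SHAM difference in change or interval for it is defined for any outcome. A true a-tDCS benefit on top of a clear SHAM gain would contradict the hypothesis as written.

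The size can only be illustrated. Compared with a direct interval, an overlap reading of the planned intervals would lose detection of a 2-SD benefit (36% against about 55%, or 83% with a shared baseline) without depending on the SHAM gain. These rates rest on independent normal scores, five per phase, equal baselines and rules that the plan does not state. The documents do not support the inference that the planned analysis is invalid, or that the data for a direct contrast would be missing.

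**What to change.** 1. Reword Hypothesis 2: *improvement from baseline is larger after REAL than after SHAM*.
2. In the Aim 2 analysis, report for each participant and outcome (REAL post − REAL pre) − (SHAM post − SHAM pre) with a 95% interval. State which sessions form each pre value (the initial pre-treatment days or post-washout measurements). For accuracy, give the difference in change, or the difference in effect size using one common baseline SD.
3. List the four participant differences with their mean and spread, as descriptive input to the future sample size, and show that sample size over a range of SDs.
4. Keep the plots, visual inspection and benchmarks.
5. State that the estimate is descriptive, that the interval assumes independent sessions and is too narrow under positive autocorrelation, and that the contrast remains confounded with the fixed SHAM-REAL order, practice and word list.

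The cost is one reworded hypothesis, a revised analysis paragraph and slightly more analysis of data already planned. The intervals will be wide, about ±1.9 session SDs, and the confounding stays.

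### One sham block followed by one real block per participant, in the same order for all four, means the REAL-SHAM comparison cannot separate a-tDCS from period, and Aim 2 is not limited accordingly

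*Combined protocol and SAP*

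**What the plan says.** The Treatment Design section describes a single-subject crossover with a washout of at least four weeks. It fixes the order: "A SHAM-REAL sequence will be used across all" participants. Both blocks contain the same behavioural naming therapy, and recruitment stops at four participants. The section concedes that a common order may introduce order effects. Its reason for not counterbalancing is that, across "participants, the small number of participants makes it difficult to interpret any data that comes" from a counterbalanced presentation.

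Aim 2 sets out to identify the effectiveness of a-tDCS combined with naming treatment and to "establish a sample size for future investigations of this nature". Hypothesis 2 expects gains in working memory, naming reaction time (RT) and naming accuracy "after the real a-tDCS condition but not after the sham a-tDCS condition". The statistical section, under Aim 2, compares means and 95% confidence intervals across conditions for each subject. The section on necessary measurements says effects will be compared with sham. Neither gives a period term or a limit on interpretation.

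Three safeguards bear on this:

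- **RT check before REAL.** List-2 RTs from the pre-treatment "testing period (prior to the initiation of the SHAM condition) will be compared to the naming RTs" obtained after washout, to confirm that no lasting "effects remain after the SHAM condition. If performance on naming RTs is +/- 1 standard" deviation of the individual's benchmark, REAL begins; otherwise it is postponed.
- **Separate word lists.** Each condition has its own balanced 20-item list.
- **Untreated pictures.** Forty control pictures are used at baseline and post-treatment testing. The outcome section counts them: "Primary outcomes include: naming accuracy on treated and control items, naming RTs on" both kinds of item.

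**The concern.** Everyone receives REAL second, after a full week of the same cue-rehearsal therapy. Practice with the tests, cumulative therapy, recovery, fatigue or a ceiling could each make the second block differ from the first with no help from stimulation. A second-course gain is plausible on the protocol's own rationale, which treats self-generation of cues as a compensatory strategy; the first block trains it.

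Two things are at stake. A period effect could be reported as an a-tDCS effect, or could hide a real one. And Aim 2 promises a sample size for later work. If the REAL-SHAM difference were used for that, the next trial would inherit the bias.

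**Working it through.** The plan states no power, alpha or calculated sample size, so there is no figure to reproduce. The question is whether the a-tDCS effect can be estimated.

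**Inputs.** Four participants (recruitment stop); two blocks each; SHAM first and REAL second for all (Treatment Design).

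**One participant.** Write the block means as

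- SHAM: μ
- REAL: μ + π + τ

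where τ is the a-tDCS effect and π is everything else that differs in the second block. Then REAL − SHAM = τ + π. The columns for intercept, period and condition have rank 2 of 3. The rank is the same if the order is reversed, so within a person the alias comes from having one period per condition.

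**Four participants, common order.** Four subject columns plus period plus condition make 6 columns. The period and condition columns are identical (correlation 1), the rank is 5 of 6, and τ is not estimable. Adding word list gives rank 5 of 7, because list is also tied to condition; balancing the lists limits that part.

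**Does the RT check break the alias?** It covers naming RT only. Accuracy, working memory and motor speech are not gated. It can reveal a lasting RT shift, but it precedes the second course and so cannot show a better response to that course.

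**Do the untreated pictures break it?** Suppose they are tested in both blocks. There are then four naming changes: treated and untreated, by block.

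- With terms for intercept, treated, block drift and a-tDCS on treated items, the rank is 4 of 4. A drift common to both kinds of item is removed.
- Adding a second-course gain on treated items gives rank 4 of 5, because that column is the same as the a-tDCS column. The alias returns.

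The first result also assumes that a-tDCS does not lift untreated items. The Stimuli section allows for generalisation, and if it occurs the subtraction removes part of the effect. Working memory and motor speech have no untreated comparator.

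**Illustration only.** Assume zero a-tDCS effect and five independent, trend-free, normal post-session scores per block. One participant's two 95% intervals then separate toward REAL in 0.3%, 1.5%, 6% and 35% of cases at a period shift of 0, 0.5, 1 and 2 session SDs. At 2 SD the figure falls to 15% with a trend of 0.5 SD per day in both blocks, and rises to 53% with lag-1 correlation of 0.5. The scores follow successive therapy days, so independence without trend is doubtful. Interval separation is also not a rule that the plan states.

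**If the difference were used for sizing.** Let π = fτ. Required n varies as 1/effect², so planned n / needed n = 1/(1+f)². For assumed f = +0.25 this is 1/1.5625 = 0.64; for f = −0.25 it is 1/0.5625 = 1.78.

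**The case against.** The strongest reply is that the limitation is disclosed and reasoned. The protocol names order effects, explains its choice, plans no hypothesis test of the contrast and relies on visual inspection. Its stated primary purpose is feasibility and safety. Hypothesis 2 is worded as improvement after one condition and not the other, and a numerical REAL-SHAM estimate is never defined.

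Much of this stands. It explains the order and keeps the point modest. It does not limit what Aim 2 concludes: effectiveness is still the stated aim, sham is still the comparator, and naming, working memory and motor speech are listed as primary outcomes.

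A reader might infer several stronger things that the documents do not support:

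- **That the fixed order is the whole fault and counterbalancing would cure it.** The analysis is per subject, and each individual contrast stays confounded in either order. Two participants per sequence would make only a group-average effect estimable (rank 6 of 6), with 2 residual degrees of freedom, or 1 if list is crossed and modelled. The plan has no group analysis. Carry-over from REAL to SHAM would also become possible, and the washout check is written only for SHAM to REAL.
- **That working memory, motor speech and accuracy lack a new baseline before REAL.** The text states a post-washout retest only for list-2 RT, but the treatment schedule is in Figure 1, which is not shown. This is a question, not a gap.
- **That the future trial will be sized from this difference.** The documents do not say so.
- **That a particular error rate applies.** The simulated percentages move widely with assumptions that the plan does not settle.

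**Conclusion.** The point holds as a limit on interpretation. Observed REAL-SHAM difference = a-tDCS effect + period or second-course effect, with either sign possible for the second term. That follows from the stated schedule alone and needs no distributional assumption. The amount of bias cannot be given, because the documents contain no period-effect size; the percentages and sample-size ratios above are illustrations.

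The exposure differs by outcome. Naming has partial protection from the untreated pictures (if tested in both blocks), and naming RT also from the check before REAL. Working memory and motor speech have neither. Aim 1 does not depend on the contrast. This should be corrected, but it does not undermine the feasibility and safety purpose.

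**What to change.** Keep the fixed order and make three changes:

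1. Restate Aim 2 and Hypothesis 2 as descriptive change within each block. State that a REAL-SHAM difference cannot be attributed to a-tDCS separately from period.
2. Where control pictures are tested in both blocks, report treated-minus-untreated naming change by block, and set list-2 RT before SHAM and after washout beside it.
3. State that the REAL-SHAM difference will not serve as the effect size for the future sample size named in Aim 2.

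All three are changes of wording and reporting. The price is a weaker Aim 2 claim.

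One question for the investigators: does Figure 1 schedule working memory, motor speech, naming accuracy and control pictures again before REAL? Change in the REAL block needs its own baseline. If it does, saying so in the text is enough. If it does not, that should be stated when results are reported, or the tests added to the existing post-washout check at the cost of testing time.

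Counterbalancing is a trade-off for the investigators and not part of this fix.
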